5. RANDOMISED CONTROLLED STUDY

Aim: To evaluate the effect of a soluble fibre supplement in glucose metabolism in pregnant women at high risk of developing gestational diabetes.

Study methodology: 12 week randomised, placebo-controlled, single-blinded study.

Intervention: Women will first be categorised according to their glycaemic status into two groups: GDM and glucose tolerant women. Afterwards, each group will be randomised into two groups and given either

- 1) Fibre supplement (Guar gum)
- 2) Placebo (Cellulose)

The participants will take the dietary supplement three times a day for 12 weeks. They will receive regular antenatal control according to NICE guidelines recommendations. Compliance will be addressed by weekly phone calls.

Number of volunteers: The number of participants will be arbitrarily define as no data of this type of intervention exists in this cohort. 40 participants will be recruited. Previous studies, outside pregnancy, have observed metabolic effects in samples of 15-40 subjects.

Recruitment: Women will be recruited in the antenatal clinic at Queen Charlotte and Chelsea's Hospital. An information sheet will be provided to eligible women in the first antenatal visit to explain the purposes of the study. Women who decide to take part will be asked to sign a consent form.

Randomisation: Initially women will be categorised according to glycaemic status in two cohorts: **Glucose tolerant** and **Early gestational diabetes (GDM)** cohort. Each of the two cohorts will then be independently randomised to either intervention or standard care using the sealed envelope website. Guar gum (intervention) and cellulose (placebo) will be provided in identical packed sachets.

STUDY OUTCOME MEASURES

PRIMARY OUTCOME MEASURES

- Glucose values at 0 and 120 minutes during an OGTT performed at 28 weeks in the glucose tolerant group.
- Glycaemic control assessed by need of insulin treatment (yes/no), days to insulin treatment and total insulin dose.

SECONDARY OUTCOME MEASURES

Assessing insulin sensitivity and insulin secretion at 28 weeks of pregnancy in the glucose tolerant cohort of women through validated indices using glucose and insulin (or C-peptide) values derived from the OGTT.

- Insulin sensitivity will be assessed using the Matsuda formula (18).
- Insulin secretion will be assessed by second-void fasting UCPCR as described by McDonald et al (19).

In the gestational diabetes cohort, where a second OGTT will not be performed, parameters of insulin resistance (HOMA_IR index) and secretion could be assessed using urinary C-peptide obtained from a fasting second-void urine sample at 28 weeks gestation, as described by Oram (20), although these measurements have not been validated in pregnancy.

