1. STUDY SUMMARY

TITLE The use of soluble fibre for the prevention of gestational diabetes among high-risk women. A pilot study.

AIMS The primary aim of this study is to evaluate the effect of a soluble fibre supplement in the development of gestational diabetes in women at high-risk. The secondary aim will be to evaluate the effect of the soluble fibre supplement on glycaemic control in high-risk women who develop gestational diabetes in early pregnancy.

DESIGN We plan to conduct a randomised single-blinded controlled study to evaluate the effect of the consumption of soluble fibre, from early to mid-pregnancy, on the incidence of gestational diabetes, insulin sensitivity, insulin secretion and metabolic control in GDM diagnosed participants.

POPULATION We will be studying women with diagnosis of gestational diabetes in previous pregnancies, (considered as high-risk) aged >18 years.

ELIGIBILITY Women over 18 years old with a history of gestational diabetes in previous pregnancies will be eligible to apply to this study. After first assessment, eligible women will be split according to their glycaemic status in women with and without early gestational diabetes.

TREATMENT Participants in the treatment arms will be taking 5 gr of Guar gum fibre supplement with meals three times a day (total daily 15 g). Participants in the placebo arms will be taking 5 gr of Cellulose three times a day (total daily dose 15 g).

DURATION Participants will be involved for 12 weeks.

OUTCOME MEASURES

In women with normal glucose tolerance at first assessment:

Primary outcome: Gestational diabetes (yes/no) at 28 weeks gestation.

Secondary outcomes: Insulin sensitivity and insulin secretion at 28 weeks gestation.

In women with early gestational diabetes (diagnosed at first assessment):

Primary outcome: Glycaemic control assessed the need of insulin treatment (yes/no)

Secondary outcomes: In women requiring insulin treatment: days-to-insulin and total daily insulin dose.

INTRODUCTION

GESTATIONAL DIABETES

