- Women willing to participate in the study will be additionally requested to provide a second urine sample after the 120 min during the OGTT. When bloods are taken will also request HbA1c as part of the study's investigations.
- An OGTT to test for early GDM will be performed as part of routine care. During the OGTT blood samples are taken at 0 and 120 minutes. Additionally to glucose, which is normally measure during the OGTT, for study purposes we will request serum C-peptide at these time points.

Baseline insulin sensitivity and insulin secretion will be estimated through validated indices using serum glucose, insulin (or C-peptide) and urinary C-peptide.

After the participants have agreed to take part in the study and consent has been signed, data regarding anthropometrics, demographics and medical history will be collected. This information will be obtained by reviewing the participant's medical notes.

Anthropometric measurements will be recorded at the first antenatal routine visit, including: pre-pregnancy weight, weight at first visit and height. BMI will be calculated with this data.

Demographics, personal and medical history will be extracted from medical records, including: maternal age, ethnicity, education, smoking during pregnancy, medical history (hypertension, PCOS, other relevant condition), obstetric history (parity, stillbirth, macrosomia, pre-eclampsia).

3rd visit (Randomisation)

[figure not shown]
After obtaining the results from the OGTT, women will be categorised by their glycaemic status and divided into two independent cohorts:

- Women diagnosed with gestational diabetes (according to NICE guidelines 2015 diagnostic criteria): **early GDM** cohort
- Women with normal glucose tolerance or impaired glucose tolerance but not fulfilling GDM criteria: **Glucose tolerant** cohort.

Women from each cohort will be randomised into two groups after the results of the OGTT are obtained:

- Intervention group: Guar gum fibre supplement
- Placebo group: Cellulose supplement

Women will take the fibre supplement 3 times a day (with each main meal) until the 28th week of pregnancy when they will be re-evaluated.

4th visit (28th weeks gestation)

Glycaemic status will be assessed at 28 weeks gestation in the two cohorts of women participating in the study:

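### Section 5 names different primary outcomes from the Summary and Section 9 (up to five measures against two), and nothing says which list governs

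*Combined protocol and SAP*

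**What the plan says.** **Section 5, primary outcome measures.** There are two bullets. The first is "Glucose values at 0 and 120 minutes during an OGTT performed at 28 weeks in the glucose tolerant group". The second, which by its content belongs to the early GDM cohort, is "Glycaemic control assessed by need of insulin treatment (yes/no), days to insulin treatment and total insulin dose". GDM yes/no is in neither the primary nor the secondary list of that section.

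**Study Summary, outcome measures.** For women with normal glucose tolerance at entry: "Primary outcome: Gestational diabetes (yes/no) at 28 weeks gestation". For women with early GDM, the primary is need for insulin (yes/no) alone, followed by "Secondary outcomes: In women requiring insulin treatment: days-to-insulin and total daily insulin dose".

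**Section 9.** The named primary outcomes are GDM yes/no and need for insulin yes/no, each analysed by logistic regression. A days-to-treatment analysis in insulin starters is described as additional. The 28-week glucose values and insulin dose have no named analysis, although a general sentence assigns numeric variables to a t test or Mann-Whitney test.

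**Section 6, 4th visit.** The diagnosis of GDM is called the endpoint for the glucose tolerant cohort. For early GDM, need, days and dose are listed without ranking.

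**Aim.** Section 5: "To evaluate the effect of a soluble fibre supplement in glucose metabolism in pregnant women at high risk of developing gestational diabetes". Summary: the "primary aim of this study is to evaluate the effect of a soluble fibre supplement in the development of gestational diabetes".

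**The concern.** The same trial has two lists of primary outcomes. In the glucose tolerant cohort, one list compares two continuous glucose values and the other compares the proportions with GDM. In the early GDM cohort, one list has three measures at primary level and the other has one.

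Two things are at stake. First, an analyst following Section 5 and an analyst following Section 9 could report different primary results from the same data, and the choice could be made once results are known. Section 9 says that the researchers are not blinded; this makes such a choice easier but does not cause the problem. Second, days to insulin and dose are defined only in women who start insulin. That subset forms after randomisation and may itself be changed by the supplement, so a comparison within it is not a comparison of the randomised arms.

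**Working it through.** **No figure to reproduce.** Sections 5 and 9 call the sample of 40 arbitrary and give no power calculation. The documents state no alpha, no cohort split and no insulin rate. The contradiction rests on the text. The numbers below only show its size, under stated assumptions.

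**Step 1. Count the measures labelled primary.**

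| | Glucose tolerant | Early GDM | Total |
|---|---|---|---|
| Section 5 | 0 min glucose, 120 min glucose | need, days, dose | 2 + 3 = 5 |
| Summary | GDM yes/no | need | 1 + 1 = 2 |
| Section 9 | GDM yes/no | need | 1 + 1 = 2 |

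Only need for insulin is primary in all three places.

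**Step 2. Are the two glucose tolerant versions the same endpoint?** Section 6, Assessments (i), diagnoses GDM if fasting glucose exceeds 5.6 mmol/L and/or 120 min glucose exceeds 7.8 mmol/L. GDM yes/no is therefore a function of the two glucose values, but it is a different variable, with a different effect measure (odds ratio against difference in level) and a different test.

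**Step 3. Chance of at least one false-positive primary.** Assume 5% per test. The upper bound is the number of tests times 0.05: 2 × 0.05 = 10% and 5 × 0.05 = 25%.

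For the two binary primaries, assume 10 per arm in each cohort (an even split of 40) and event rates of 20-60%. Over two independent cohorts the chance is 1 − (1 − size)²:
- Pearson chi-square: exact size 0.030 to 0.042 per cohort, giving 0.059 to 0.083, about 6-8%.
- Logistic regression, likelihood-ratio test: exact size 0.052 to 0.087 per cohort, giving 0.102 to 0.167, about 10-17%. This passes the 10% bound because the test does not hold 5% in samples this small.

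**Step 4. How often the two glucose tolerant versions disagree.** Simulation with 10 per arm, two normal glucose values with correlation 0 or 0.5, and GDM if either value is above a cut giving 20, 40 or 60% GDM on placebo. Disagreement means that at least one glucose value has p<0.05 and GDM yes/no does not, or the reverse. With glucose 0.5 SD lower at both times, this happens in 21-32% of trials. With no effect it is 9-11% (chi-square for GDM), mostly ordinary false positives in one test or the other.

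**Step 5. Whether a starters-only comparison can reach significance.** With a and b starters in the two arms, the smallest two-sided exact Mann-Whitney p is 2/C(a+b, a). With 3 and 3 it is 2/20 = 0.10; with 4 and 4 it is 2/70 = 0.029. Summing binomial probabilities over all (a, b) where this exceeds 0.05, or where an arm has no starters, at an assumed 40% insulin rate:

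| Early GDM women per arm | Chance that p≤0.05 is out of reach |
|---|---|
| 7 | 86% |
| 10 | 46% |
| 13 | 16% |

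With 10 per arm the figure is 97% at a 20% insulin rate and 3% at 60%.

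**Step 6. What the binary primary gives up.** At an assumed 0.8 SD difference and 10 per arm, power is about 40% for one glucose value, 43-49% for either value with Bonferroni, and 21-40% for GDM yes/no by likelihood ratio.

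**The case against.** The best defence is that the trial is a declared pilot with no stated alpha, so familywise error is not something the plan claims to control. Moreover, Section 9, where one looks for the analysis, agrees with the Summary on one primary per cohort, and GDM is derived from the same glucose values. Much of this stands. It limits the weight of the error rates and makes clear which way to reconcile. It does not remove the conflict: Section 5 is the protocol's own list of outcome measures, and nothing ranks it below Section 9. Pilot status explains the arbitrary sample size, not two different primaries.

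A reader might infer more than the documents support:
- *That the 4th visit also contradicts Section 5 throughout.* It never uses the word primary. It conflicts only for the glucose tolerant cohort; for early GDM it lists Section 5's three items unranked.
- *That the two aims contradict each other.* Glucose metabolism is the broader phrase, and the Summary's design paragraph also covers insulin sensitivity, secretion and metabolic control. This is a minor wording point.
- *That Section 5 must be read as five primaries.* Taken as one composite per bullet it has two. The glucose tolerant primary would still differ, and days and dose would still sit at primary level.
- *That 25% is the error rate.* It is only an upper bound, and the rate for two primaries depends on which test is used for the binary outcomes.
- *That keeping GDM yes/no costs most of the power.* That impression comes from setting a conservative chi-square test against the better of two unadjusted glucose tests. On fairer terms the gap is smaller (Step 6).

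**Conclusion.** The contradiction is established from the text and needs no assumption: up to five primary measures in Section 5 against two in the Summary and Section 9, different primary variables in the glucose tolerant cohort, and no rule of precedence in the text available. It should be corrected before any outcome data are analysed. The main ground is glucose values against GDM yes/no. The second is that days to insulin and dose, as primaries, compare a subset formed after randomisation.

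The sizes are illustrative. They rest on an assumed 5% per test, 10 women per arm unless another number is shown, normally distributed glucose, and assumed event rates and effect sizes. The starters-only figure in particular moves widely with the cohort split and the insulin rate, neither of which the documents give.

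**What to change.** Change Section 5's primary list to match the Summary and Section 9:
- Glucose tolerant cohort: GDM yes/no at 28 weeks as the single primary.
- Early GDM cohort: need for insulin (yes/no) as the single primary.
- Secondary: the 0 and 120 min glucose values, days to insulin and insulin dose.
- Align Section 5's aim with the Summary's primary and secondary aims.

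Optional: analyse each 28-week glucose value by linear regression on arm, adjusted for its own baseline OGTT value. The baseline values already exist, since Section 6 (2nd visit) says "During the OGTT blood samples are taken at 0 and 120 minutes". If this is adopted, Section 9 should state that it replaces the t test or Mann-Whitney test for those values, so that they do not have two methods.

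The cost is a few lines of wording, with no new visits, samples or participants. The downside is that fewer outcomes can be called primary and GDM yes/no is somewhat less sensitive than a glucose value. Section 9 as written already accepts that, and the glucose values are still reported. Choosing a glucose value as the primary instead would be a trade-off for the sponsor, outside this correction.

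Relabelling leaves two definitions to tidy in the same edit. Dose is described as daily in the Summary, as a total in Section 5, and per kg in Section 6. In Section 6, Assessments (iv), need for insulin is determined at 28 weeks, but days and dose apply to insulin use at any time in follow-up.

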6. ASSESSMENT AND FOLLOW UP

Women will be assessed by the researchers at four different visits. At the first antenatal visit, the general care team will mention the study, if the patient consents, she will then be approached by the researchers to explain the study protocol. At the second visit, when the OGTT is performed, women who decided to take part in the study will sign the consent form. At the next antenatal visit where results from the OGTT are explained, women included will be randomised. The last research visit will take place at 28 weeks gestation. Additionally, they will be contacted weekly, by telephone to assess compliance and confirm willingness to participate in the study. All participating women will continue to attend routine follow up by the Obstetrics team at the antenatal clinic. Women diagnosed with GDM in early pregnancy will continue their routine care under the Obstetric team at Queen Charlotte's Hospital. We will be collecting information regarding treatment from the notes taken at this follow-up visits.

1st visit (≤16 weeks gestation)

Women with a previous history of GDM will be considered at high risk of recurrence and will be referred to the antenatal clinic before 16 weeks of pregnancy. At this first visit, the direct care team will inform them about the study and ask them if they are willing to speak with a member of the research team. If they agree, a research team member will explain the protocol and invite them to participate in the study. An information sheet will be provided and women will have time to consider if they are willing to participate and inform the research team at their next antenatal visit.

2nd visit

Women who decide to participate will inform the research team when they attend their second antenatal visit, when an OGTT is to be performed. In this visit, women willing to participate will be asked to sign a consent form.

As part of the standard pregnancy care, these women will be booked for GDM early screening. The following investigations will be performed as part of their usual NHS care:

- Blood tests: full blood count, renal function. GAD antibodies can be requested in women in whom type 1 diabetes is suspected.
- Urine sample to test for proteinuria, glycosuria, leucocytes and nitrates.
- Women willing to participate in the study will be additionally requested to provide a second urine sample after the 120 min during the OGTT. When bloods are taken will also request HbA1c as part of the study's investigations.
- An OGTT to test for early GDM will be performed as part of routine care. During the OGTT blood samples are taken at 0 and 120 minutes. Additionally to glucose, which is normally measure during the OGTT, for study purposes we will request serum C-peptide at these time points.

Baseline insulin sensitivity and insulin secretion will be estimated through validated indices using serum glucose, insulin (or C-peptide) and urinary C-peptide.

After the participants have agreed to take part in the study and consent has been signed, data regarding anthropometrics, demographics and medical history will be collected. This information will be obtained by reviewing the participant's medical notes.

Anthropometric measurements will be recorded at the first antenatal routine visit, including: pre-pregnancy weight, weight at first visit and height. BMI will be calculated with this data.

Demographics, personal and medical history will be extracted from medical records, including: maternal age, ethnicity, education, smoking during pregnancy, medical history (hypertension, PCOS, other relevant condition), obstetric history (parity, stillbirth, macrosomia, pre-eclampsia).

3rd visit (Randomisation)

[figure not shown]
After obtaining the results from the OGTT, women will be categorised by their glycaemic status and divided into two independent cohorts:

- Women diagnosed with gestational diabetes (according to NICE guidelines 2015 diagnostic criteria): **early GDM** cohort
- Women with normal glucose tolerance or impaired glucose tolerance but not fulfilling GDM criteria: **Glucose tolerant** cohort.

Women from each cohort will be randomised into two groups after the results of the OGTT are obtained:

- Intervention group: Guar gum fibre supplement
- Placebo group: Cellulose supplement

Women will take the fibre supplement 3 times a day (with each main meal) until the 28th week of pregnancy when they will be re-evaluated.

4th visit (28th weeks gestation)

Glycaemic status will be assessed at 28 weeks gestation in the two cohorts of women participating in the study:

- Women from the **Glucose tolerant cohort** will undergo a second OGTT. Blood and urine samples will be collected at 0 and 120 minutes. Glycaemic status will then be assessed with the endpoint being the diagnosis of GDM (yes/no). Insulin sensitivity and insulin secretion will be estimated using the same parameters as in the first visit. As part of the study, women will be weight to calculate BMI and gestational weight gain at 28 weeks gestation. The research team will have their last face to face visit with the participant to discontinue the intervention and answer any potential questions about the study.
- In women in the **Early GDM cohort**, glycaemic control will be assessed by the need of insulin treatment (yes/no) and in those requiring insulin the days-to-treatment (insulin) and total insulin dose will be recorded. Data will be obtained by reviewing medical records. As part of the study, women will be weight to calculate BMI and gestational weight gain at 28 weeks gestation. The research team will have their last face to face visit with the participant to discontinue the intervention and answer any potential questions about the study.

PROCEDURES

Women will be advised to fast for 10 hours the night before the oral glucose tolerance test. They will also be advised not to restrict carbohydrate ingestion the three days prior to the OGTT. At the antenatal clinic, blood samples will be collected at baseline (0 min) and at 120 min after the administration of an oral load of 75 g of glucose.

In the baseline sample other parameters will also be determined. Creatinine and HbA1c will measure in all participants and GAD antibodies will be requested in women in whom type 1 diabetes is suspected.

Serum insulin and C-peptide will be collected at 0 and 120 min during the OGTT.

Women will be advised to void their first urine before attending the antenatal clinic. Second-void fasting urine sample will be collected at 0 min during the OGTT. A second urine sample will be collected at 120 min. Urinary C-peptide will measure in these samples will be transfer to boric acid containers, the aliquoted into 1 ml cryotubes and stored at -80 °C until analysis. Serum creatinine will be collected at baseline (0 min) and measure in the central lab. The urinary C-peptide creatinine ratio (UCPCR) will be calculated using these data.

ASSESSMENTS

(i) Gestational diabetes

Gestational diabetes will be diagnosed if fasting plasma glucose >5.6 mmol/L and/or 120 min plasma glucose >7.8 mmol/L after the glucose load administered in the OGTT. Women with fasting plasma glucose <5.6 mmol/L and 120 min plasma glucose <7.8 mmol/L will be classified as “Glucose tolerant”.

(ii) Insulin sensitivity

Insulin sensitivity will be assessed using the Matsuda index as originally described (18) (Equation 1) and using two modified Matsuda equations in which insulin is substitute by either serum or urinary C-peptide (21,22) (Equations 2 and 3).

Equation 1.

$$\text{ISOGTT} = 10,000 / \sqrt{[\text{FPG} \times \text{fasting insulin}] \times [\text{mean glucose} \times \text{mean insulin during OGTT}]}$$

Equation 2.

$$\text{ISOGTT-} \text{C-pep} = 500,000 / \sqrt{[\text{FPG} \times \text{FsC-pep}] \times [\text{mean glucose} \times \text{mean sC-pep during the OGTT}]}$$

Equation 3.

$$\text{ISOGTT-UCPCR} = 500,000 / \sqrt{[\text{FPG} \times \text{UCPCR}_{\text{pmol}/\text{mmol}}] \times [\text{mean glucose} \times \text{mean UCPCR during the OGTT}]}$$

* FPG= fasting plasma glucose. FsC= fasting serum C-peptide. FUCPCR= fasting urinary C-peptide creatinine ratio.

(iii) Insulin secretion

[figure not shown]
Insulin secretion will be estimated by the UCPCR obtained using the fasting second-void urine sample, as it is strongly correlated with serum insulin, serum C-peptide (19) and 24-h urinary C-peptide (20).

Insulin response will be estimated using the UCPCR calculated with 120 min post-OGTT urine sample, as it is strongly correlated with the C-peptide and insulin area under the curve (19).

(iv) Need of insulin treatment, Days to insulin treatment and Total insulin dose

Medical records of women in the Early GDM cohort will be reviewed in order to determine the need of insulin treatment (yes/no) at 28 weeks gestation. In women requiring insulin treatment at any time during follow up, days-to-insulin treatment, calculated from randomisation day to the day insulin treatment is prescribed, and total insulin dose, calculated as the total dose of insulin international units (IU) divided by weight in Kg (insulin UI/Kg), will be recorded

Timeline for randomised controlled study

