The beneficial effects of Guar gum on glycaemic control can possibly be explained through various mechanisms. Firstly, the impact on glycaemic control over the first two hours after consumption of food that possibly relates to the impact of soluble viscous fibres on delaying gastric emptying and slowing the digestion of carbohydrate in the small intestine. There is an additional benefit as Guar gum is fermented by the colonic microbiota to short-chain fatty acids which are recently been shown to have important benefits on beta-cell function presumably by stimulating the production of GLP1 (10).

THE ROLE OF HIGH-FIBRE DIETS IN THE PREVENTION AND TREATMENT OF GESTATIONAL DIABETES

In pregnancy, a high dietary fibre intake has been associated with a lower risk of GDM (11), and in healthy pregnant women, a low GI diet has been associated with lower birth weight and a lower

percentage of large for gestational age newborns (12). As for women who develop GDM, high-fibre diets have been associated with an improvement in perinatal outcomes such as macrosomia (12–14) and risk of C-section (13). In this group of women, high-fibre diets have also to significantly reduce the need to commence insulin treatment (13–15). Despite the documented benefits of a high-fibre diet, as women progress through pregnancy there are often changes in food perception and acceptability which makes compliance to specific diets often difficult. A dietary supplement that can be consumed with meals could be an attractive alternative for complying with the recommended dietary fibre requirements. In pregnancy, Guar gum has shown to reduce postprandial glycaemia after an OGTT (16) and in one study, long term consumption of 10 gr a day showed to decrease both fasting and postprandial glycaemia (17). Therefore, it could be considered in the treatment of women with gestational or who are at high risk of developing the condition.

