8. ADVERSE EVENTS

Adverse Event (AE): Any untoward medical occurrence in a patient or clinical study subject.

Serious Adverse Event (SAE): Any untoward and unexpected medical occurrence that: results in death, is life-threatening, requires hospitalisation, results in persistent or significant disability or incapacity or a congenital abnormality or birth defect

Medical judgement should be exercised in deciding whether an AE is serious in other situations. Important AEs that are not immediately life threatening or do not result in death or hospitalisation but may jeopardise the subject or may require intervention to prevent one of the other outcomes listed in the definition above, should also be considered serious.

REPORTING PROCEDURES

All adverse events should be reported. Depending on the nature of the event the reporting procedures below should be followed. Any questions concerning adverse event reporting should be directed to the Chief Investigator in the first instance.

Non serious AEs

All such events, whether expected or not, should be recorded.

Serious AEs

An SAE form should be completed and faxed to the Chief Investigator within 24 hours. However, relapse, death and hospitalisations for elective treatment of a pre-existing condition do not need reporting as SAEs. All SAEs should be reported to the sponsor.

All SAEs should be reported to the Bromley Research Ethics Committee where in the opinion of the Chief Investigator the event was:

‘Related’, i.e. resulted from the administration of any of the research procedures; and

‘Unexpected’, i.e. an event that is not listed in the protocol as an expected occurrence.

Reports of related and unexpected SAEs should be submitted within 15 days of the Chief Investigator becoming aware of the event, using the NRES SAE form for non-IMP studies.

Local investigators should report any SAEs as required by their Local Research Ethics Committee and/ or Research and Development Office.

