9. STATISTICS AND DATA ANALYSIS

Data handling and analysis will be carried out by SPSS version 20.0 version.

No power calculation to decide sample size will be used. The number of participants has been arbitrarily defined, as it is a pilot study. We aim to recruit 40 women.

Before randomisation, women will be categorised according to their glycaemic status in two cohorts: Glucose tolerant and GDM. Each of these two cohorts will be randomly allocated into the

intervention (soluble fibre supplement) and control (placebo) group. Randomisation will be by sealed envelopes. Participants but not researchers will be blinded as to the type of intervention prescribed.

Differences between group in each cohort will be assessed using Student t test or Mann-Whitney U test for numeric variables depending on distribution; χ^2 will be used for categorical variables.

In the Glucose tolerant women cohort:

For the primary outcome, GDM (yes/no), logistic regression analysis will be performed.

For the secondary outcomes, insulin sensitivity and insulin secretion, linear regression analysis will be performed.

In the early GDM cohort:

For the primary outcome, need for insulin treatment (yes/no), logistic regression analysis will be performed. Additionally days-to-treatment analysis will be performed for those participants starting insulin therapy during follow up.

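### Adverse events must be recorded, but no method of eliciting them is given and researchers know the allocation, so event counts by arm would be unreliable

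*Combined protocol and SAP*

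**What the plan says.** **Duty to record.** Section 8 (Adverse Events) states "All adverse events should be reported" and, for non-serious events, "All such events, whether expected or not, should be recorded". It does not say who asks, when, with what question, or how severity is graded.

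**Weekly calls.** Section 5 says "Compliance will be addressed by weekly phone calls". Section 6 adds a second purpose: "Additionally, they will be contacted weekly, by telephone to assess compliance and confirm willingness to participate in the study".

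**28-week visit.** Section 6 (4th visit) lists the OGTT with blood and urine samples (glucose tolerant cohort) or insulin treatment data from records (early GDM cohort). In both cohorts it adds weight, stopping the supplement and answering the participant's questions. No event enquiry is listed.

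**Clinic notes.** Section 6 has the team take treatment information from routine follow-up notes. Adverse events are not mentioned there.

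**Blinding.** Section 9: "Participants but not researchers will be blinded as to the type of intervention prescribed".

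**Outcomes and analysis.** Tolerability is not among the outcomes in the Study Summary or section 5, and section 9 names no safety analysis.

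**The concern.** A duty to record events does not by itself produce complete records. If nobody is told to ask, mild and moderate symptoms tend to reach the file only when a woman mentions them or when they lead to treatment. Here such symptoms are foreseeable: the Introduction attributes the action of guar gum partly to slower gastric emptying and to fermentation in the colon, both of which point to gastrointestinal effects.

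The open allocation adds a second problem. A researcher who knows that a woman takes guar gum may probe harder, or may discount symptoms as expected. Either would make recording differ by arm.

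Two things are at stake. Event counts by arm could mislead anyone planning a larger trial. Reasons for missed sachets may also be lost, so that poor compliance could not be linked to intolerance. The Introduction proposes a supplement because special diets are hard to follow in pregnancy, so that link matters to the trial's own rationale.

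**Working it through.** **1. The passages side by side**

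| Contact or source after randomisation | Stated content | Event enquiry described? |
|---|---|---|
| Weekly call (sections 5 and 6) | Compliance, willingness | No |
| 28-week visit (section 6) | Tests or insulin data, weight, stopping the supplement, questions | No |
| Routine clinic notes (section 6) | Treatment information | No |
| Withdrawal (section 7) | No reason required | No |
| Section 8 | Duty to report and record | Duty stated, method not stated |

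Section 8 also defines an unexpected event as "an event that is not listed in the protocol as an expected occurrence", but the text available contains no list of expected events. It therefore gives no prompt for what to ask.

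**2. Inputs for an illustration**

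The plan has no tolerability figure to reproduce. Section 9 calls the total of 40 arbitrary and gives no power calculation. The following are assumptions: 1:1 allocation (no ratio is stated), both cohorts pooled, no dropout (so 40/2 = 20 per arm), two-sided alpha of 0.05, and all event rates and capture shares.

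**3. Effect of incomplete capture**

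Recorded rate = true rate × share captured.

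- *Equal under-capture.* True rates 20% and 50%, half captured in each arm: 0.20 × 0.5 = 10% and 0.50 × 0.5 = 25%. The difference shrinks from 30 to 15 points. Exact Fisher power at 20 per arm falls from 41% to 14%.
- *Unequal capture.* True rate 40% in both arms, captured at 50% and 75%: 0.40 × 0.50 = 20% and 0.40 × 0.75 = 30%. A 10-point difference appears where none exists.
- *No recorded events.* For 0 of 20 the one-sided 95% upper limit is 1 − 0.05^(1/20) = 13.9%, provided every event was captured. If only half were, the limit applies to 0.5 × the true rate, so the true rate could be as high as 13.9%/0.5 = 27.8%.

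**4. What full capture would give**

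95% half-width for a risk difference = 1.96 × √[p₁(1−p₁)/20 + p₂(1−p₂)/20].

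- 20% vs 20%: 1.96 × √0.0160 = 24.8 points
- 20% vs 40%: 1.96 × √0.0200 = 27.7 points
- 20% vs 50%: 1.96 × √0.0205 = 28.1 points

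With full capture, Fisher power at 20 per arm is 19% for 20% vs 40% and 41% for 20% vs 50%. If the two cohorts were of equal size and analysed separately (10 per arm), it is 6% and 13%. By the normal approximation, 80% power would need 82 or 39 women per arm respectively. Better elicitation would therefore make the description sound, but not precise.

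**The case against.** The strongest reply is that the plan is silent on method, and silence does not show that nobody will ask. A reader might infer that the calls cover compliance and willingness and nothing else, or that events can reach the file only if volunteered. The documents do not support either reading. Section 6 gives the calls' purposes without saying that they are exhaustive, and section 8 places a general duty to record in both arms. Routine obstetric notes, and the reasons that section 10 (Consent) wants recorded when a clinician departs from protocol treatment, could bring treated events to light. None of these routes is described as event collection, however, and they would mostly miss mild symptoms. The method of ascertainment remains unspecified.

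A reader might also infer that the pilot cannot compare tolerability at all. That goes too far: recorded events, compliance and discontinuation can still be tabulated by arm. The event comparison would be unreliable rather than impossible, and sample size limits it as well. It is fair to add that tolerability is not a stated aim, although recording adverse events is a duty the protocol sets itself.

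Finally, a reader might take the daily amount as a measure of the problem: 15 g here against the pregnancy study in the Introduction, where "long term consumption of 10 gr a day showed to decrease both fasting and postprandial glycaemia", a ratio of 15/10 = 1.5. The Introduction also cites 15 g a day for 48 weeks in type 2 diabetes. Section 10 says that the trial product is partially hydrolysed, and the form used in the 10 g study is not given. The ratio may not compare like with like, and it says nothing about how events are collected.

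**Conclusion.** The concern stands as a gap in how adverse events are ascertained, not as an absence of collection. Sections 5, 6 and 8 together require recording without describing elicitation, and section 9 leaves researchers aware of allocation. Mild and moderate events, gastrointestinal ones above all, are likely to be under-recorded and may be recorded unequally by arm.

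The size cannot be estimated from the documents. Under the assumed capture shares, unequal recording alone could create a 10-point difference, and halving capture doubles the true rate that remains compatible with no recorded events. Even with full capture, about 20 per arm gives half-widths of roughly 25 to 28 points, so the data can only be descriptive.

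The point deserves action before recruitment because symptoms not asked about cannot be reliably recovered later. The objective glucose outcomes are not affected by it.

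**What to change.** In sections 5 and 6, add a fixed script to each planned weekly call, worded identically in both arms, covering:

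- any new symptom
- gastrointestinal symptoms (yes/no, with severity)
- symptoms of low glucose in women on insulin
- any hospital contact
- the reason for any missed sachets

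Repeat the script at the 28-week visit. Where existing staffing allows, have it asked by someone unaware of allocation; identical wording alone reduces unequal probing but does not remove it.

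In section 9, add a descriptive table of answers by arm with confidence intervals and without a claim of a precise comparison. Leave the reporting time for serious adverse events in section 8 unchanged, since nothing here shows a fault in it.

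**Cost.** A one-page script and a few case report form fields. It uses contacts already planned: at most 40 × 12 = 480 calls, assuming 12 calls for every woman and no withdrawals. The downside is slightly longer calls and more minor events recorded.
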